10.3.2. Pharmacokinetic Analyses

10.3.2.1. Pharmacokinetic Parameter Estimation

Pharmacokinetic parameter estimates for LY3202626 will be calculated by standard noncompartmental methods of analysis.

The primary parameters for analysis will be C_{max} , AUC from time zero to infinity ($AUC_{0-\infty}$), AUC from time zero to time t , where t is the last time point with a measurable concentration ($AUC_{0-t_{last}}$), and time of maximum observed drug concentration (t_{max}) of LY3202626. Other noncompartmental parameters, such as $t_{1/2}$, apparent total body clearance of drug calculated after extra-vascular administration (CL/F), and apparent volume of distribution during the terminal phase after extra-vascular administration (V_z/F) will be reported if evaluable based on available data.

10.3.2.2. Pharmacokinetic Statistical Inference

Pharmacokinetic parameter estimates will be evaluated to delineate relative bioavailability and food effects.

The following comparisons will be interests of statistical analysis of PK parameters:

- relative bioavailability: LY3202626 T1-12 fasted (test) versus LY3202626 R fasted (reference)
- food effect: LY3202626 T1-12 fed (test) versus LY3202626 T1-12 fasted (reference).

Log-transformed C_{max} and AUC estimates will be evaluated in a linear mixed-effects model with fixed effects for dose administration and period and a random effect for subject. The ratio of geometric least squares means and corresponding 90% CI will be presented for LY3202626

T1-12 versus LY3202626 R for analysis of relative bioavailability, and LY3202626 T1-12 administered with a high-fat meal versus LY3202626 T1-12 administered fasted for the analysis of the food effect. One model will be used for the assessment of relative bioavailability and the effect of food.

The t_{max} will be analyzed non-parametrically. Median of differences and approximate 90% CI for the median of differences will be calculated. P-values will also be calculated using a Wilcoxon signed rank test.

Additional analyses may be performed if deemed necessary.

10.3.3. *Pharmacodynamic Analysis*

10.3.3.1. *Pharmacodynamic Parameter Estimation*

Plasma concentrations of $A\beta_{1-40}$ and $A\beta_{1-42}$ will be summarized for each treatment based on the nadir concentration (C_{nadir}), the time to reach C_{nadir} (t_{nadir}), and the 24-hour average values expressed as percentage change from baseline.

10.3.3.2. *Pharmacodynamic Statistical Inference*

No formal statistical testing will be conducted.

10.3.4. *Interim Analyses*

No interim analyses are planned for this study. If an unplanned interim analysis is deemed necessary, the Lilly CP, CRP/investigator, or designee will consult with the appropriate medical director or designee to determine if it is necessary to amend the protocol.

11. References

Appendix 1. Abbreviations and Definitions

Term	Definition
Aβ	amyloid beta
AD	Alzheimer's disease
AE	adverse event: Any untoward medical occurrence in a patient or clinical investigation subject administered a pharmaceutical product that does not necessarily have a causal relationship with this treatment. An AE can therefore be any unfavorable and unintended sign (including an abnormal laboratory finding), symptom, or disease temporally associated with the use of a medicinal (investigational) product, whether or not related to the medicinal (investigational) product.
APP	amyloid precursor protein
AUC	area under the concentration versus time curve
AUC_{0-t_{last}}	area under the concentration versus time curve from time zero to time t, where t is the last time point with a measurable concentration
AUC_{0-∞}	area under the concentration versus time curve from time zero to infinity
BACE1	β-site amyloid precursor protein-cleaving enzyme
BMI	body mass index
CI	confidence interval
CL/F	apparent total body clearance of drug calculated after extra-vascular administration
C_{max}	maximum observed drug concentration
C_{nadir}	nadir concentration
complaint	A complaint is any written, electronic, or oral communication that alleges deficiencies related to the identity, quality, purity, durability, reliability, safety or effectiveness, or performance of a drug or drug delivery system.
compliance	Adherence to all the trial-related requirements, good clinical practice (GCP) requirements, and the applicable regulatory requirements.
confirmation	A process used to confirm that laboratory test results meet the quality requirements defined by the laboratory generating the data and that Lilly is confident that results are accurate. Confirmation will either occur immediately after initial testing or will require that samples be held to be retested at some defined time point, depending on the steps required to obtain confirmed results.
CP	clinical pharmacologist

CRP	clinical research physician: Individual responsible for the medical conduct of the study. Responsibilities of the CRP may be performed by a physician, clinical research scientist, global safety physician or other medical officer.
CRU	clinical research unit
CSF	cerebral spinal fluid
CV	coefficient of variation
CYP	cytochrome P450
ECG	electrocardiogram
eCRF	electronic case report form
end of trial (study)	End of trial is the date of the last visit or last scheduled procedure shown in the Study Schedule for the last subject.
enroll	The act of assigning a subject to a treatment. Subjects who are enrolled in the trial are those who have been assigned to a treatment.
enter	Subjects entered into a trial are those who sign the informed consent form directly or through their legally acceptable representatives.
ERB/IRB	ethical review board
ET	early termination
FDA	Food and Drug Administration
FSH	follicle-stimulating hormone
GCP	good clinical practice
HIV	human immunodeficiency virus
IB	Investigator's Brochure
ICF	informed consent form
ICH	International Conference on Harmonization
informed consent	A process by which a subject voluntarily confirms his or her willingness to participate in a particular trial, after having been informed of all aspects of the trial that are relevant to the subject's decision to participate. Informed consent is documented by means of a written, signed and dated informed consent form.
Investigational product (IP)	A pharmaceutical form of an active ingredient or placebo being tested or used as a reference in a clinical trial, including products already on the market when used or assembled (formulated or packaged) in a way different from the authorized form, or marketed products used for an unauthorized indication, or marketed products used to gain further information about the authorized form.

investigator	A person responsible for the conduct of the clinical trial at a trial site. If a trial is conducted by a team of individuals at a trial site, the investigator is the responsible leader of the team and may be called the principal investigator.
MEDRA	Medical Dictionary for Regulatory Activities
open-label	A study in which there are no restrictions on knowledge of treatment allocation, therefore the investigator and the study participant are aware of the drug therapy received during the study.
PD	pharmacodynamics(s)
PK	pharmacokinetic(s)
QD	once daily
R	reference formulation (12 mg capsule)
SAE	serious adverse event
screen	The act of determining if an individual meets minimum requirements to become part of a pool of potential candidates for participation in a clinical trial.
subject	An individual who is or becomes a participant in clinical research, either as a recipient of the investigational product(s) or as a control. A subject may be either a healthy human or a patient.
SUSARs	suspected unexpected serious adverse reactions
t_{1/2}	half-life associated with the terminal rate constant (λ) in noncompartmental analysis
T1-12	test formulation (12 mg tablet)
TEAE	treatment-emergent adverse event: Any untoward medical occurrence that emerges during a defined treatment period, having been absent pretreatment, or worsens relative to the pretreatment state, and does not necessarily have to have a causal relationship with this treatment
t_{max}	time of maximum observed drug concentration
t_{nadir}	time to reach nadir concentration
V_{z/F}	apparent volume of distribution during the terminal phase after extra-vascular administration

Appendix 2. Clinical Laboratory Tests

Laboratory Tests

Hematology ^a	Clinical Chemistry ^a
Hematocrit	Sodium
Hemoglobin	Potassium
Erythrocyte count (RBC)	Bicarbonate
Mean cell volume	Chloride
Mean cell hemoglobin	Glucose, random
Mean cell hemoglobin concentration	Blood urea
Leukocytes (WBC)	Total protein
Absolute counts of:	Creatinine
Neutrophils	Liver tests:
Lymphocytes	Albumin
Monocytes	Total bilirubin
Eosinophils	Alkaline phosphatase (ALP)
Basophils	Aspartate aminotransferase (AST)
Platelets	Alanine aminotransferase (ALT)
	Gamma-glutamyl transferase (GGT)
Urinalysis ^a	
Specific gravity	
pH	
Protein	Hepatitis B surface antigen ^d
Glucose	Hepatitis C antibody ^d
Ketone	HIV ^d
Bilirubin	FSH ^b
Urobilinogen	
Blood	
Nitrite	
Leukocyte	
Microscopy ^c	

Abbreviations: FSH = follicle-stimulating hormone; HIV = human immunodeficiency virus; RBC = red blood cells; WBC = white blood cells.

Note: Results of these assays will be validated by the local laboratory at the time of testing.

Additional tests may be performed or auto-calculated by the laboratory as part of its standard panel that cannot be removed. Some of the above parameters are calculated from measured values. Omission of calculated values will not be considered as a protocol violation.

a Results will be validated by the local lab at the time of testing.

b Performed at screening only, in post-menopausal women with 6-12 months of amenorrhea.

c If clinically indicated, per investigator's discretion.

d Performed at screening only. This test will be performed unless results of the same test have been obtained from the subject within the last 6 months.

Appendix 3. Study Governance, Regulatory and Ethical Considerations

Informed Consent

The investigator is responsible for:

- ensuring that the subject understands the potential risks and benefits of participating in the study.
- ensuring that informed consent is given by each subject or legal representative. This includes obtaining the appropriate signatures and dates on the ICF prior to the performance of any protocol procedures and prior to the administration of investigational product.
- answering any questions the subject may have throughout the study and sharing in a timely manner any new information that may be relevant to the subject's willingness to continue his or her participation in the trial.

Ethical Review

The investigator must give assurance that the ERB was properly constituted and convened as required by ICH guidelines and other applicable laws and regulations.

Documentation of ERB approval of the protocol and the ICF must be provided to Lilly before the study may begin at the investigative site(s). Lilly or its representatives must approve the ICF before it is used at the investigative site(s). All ICFs must be compliant with the ICH guideline on GCP.

The study site's ERB(s) should be provided with the following:

- the current IB
- ICF
- relevant curricula vitae

Regulatory Considerations

This study will be conducted in accordance with:

- 1) consensus ethics principles derived from international ethics guidelines, including the Declaration of Helsinki and Council for International Organizations of Medical Sciences (CIOMS) International Ethical Guidelines
- 2) applicable ICH GCP Guidelines
- 3) applicable laws and regulations

Some of the obligations of the sponsor will be assigned to a third party organization.

Protocol Signatures

The sponsor's responsible medical officer will approve the protocol, confirming that, to the best of his or her knowledge, the protocol accurately describes the planned design and conduct of the study.

After reading the protocol, each principal investigator will sign the protocol signature page and send a copy of the signed page to a Lilly representative.

Final Report Signature

The investigator or designee will sign the clinical study report for this study, indicating agreement with the analyses, results, and conclusions of the report.

The sponsor's responsible medical officer and statistician will sign/approve the final clinical study report for this study, confirming that, to the best of his or her knowledge, the report accurately describes the conduct and results of the study.

Data Quality Assurance

To ensure accurate, complete, and reliable data, Lilly or its representatives will do the following:

- provide instructional material to the study sites, as appropriate.
- provide training to instruct the investigators and study coordinators. This training will give instruction on the protocol, the completion of the CRFs, and study procedures.
- make periodic visits to the study site.
- be available for consultation and stay in contact with the study site personnel by mail, telephone, and/or fax.
- review and evaluate CRF data and/or use standard computer edits to detect errors in data collection.
- conduct a quality review of the database.

In addition, Lilly or its representatives will periodically check a sample of the subject data recorded against source documents at the study site. The study may be audited by Lilly and/or regulatory agencies at any time. Investigators will be given notice before an audit occurs.

The investigator will keep records of all original source data. This might include laboratory tests, medical records, and clinical notes. If requested, the investigator will provide the sponsor, applicable regulatory agencies, and applicable ERBs with direct access to the original source documents.

Data Collection Tools/Source Data

An electronic data capture system will be used in this study. The site must define and retain all source records and must maintain a record of any data where source data are directly entered into the data capture system.

Study and Site Closure***Discontinuation of Study Sites***

Study site participation may be discontinued if Lilly or its designee, the investigator, or the ERB of the study site judges it necessary for medical, safety, regulatory, or other reasons consistent with applicable laws, regulations, and GCP.

Discontinuation of the Study

The study will be discontinued if Lilly or its designee judges it necessary for medical, safety, regulatory, or other reasons consistent with applicable laws, regulations, and GCP.

Appendix 4. Blood Sampling Summary

This table summarizes the approximate number of venipunctures and blood volumes for all blood sampling (screening, safety laboratories, and bioanalytical assays) during the study. Fewer venipunctures and blood draws may actually occur, but this will not require a protocol amendment.

Protocol I7X-MC-LLCE Sampling Summary

Purpose	Maximum Blood Volume per Sample (mL)	Maximum Number of Blood Samples	Maximum Total Volume (mL)
Screening tests ^a	15	1	15
Clinical laboratory tests ^a	9	9	81
Pharmacokinetics ^b	3	59	177
Pharmacodynamics	2	57	114
Pharmacogenetics	10	1	10
Total			397
Total for clinical purposes [rounded up to nearest 10 mL]			400

a Additional samples may be drawn if needed for safety purposes.

b Includes an additional 2 samples which may be collected at additional time points during the study if warranted and agreed upon between both the investigator and sponsor.

Leo Document ID = 114c4e79-b2cf-4dc1-83b6-75b5265dbfc9

Approver: PPD

Approval Date & Time: 08-Sep-2016 20:33:51 GMT

Signature meaning: Approved

Approver: PPD

Approval Date & Time: 10-Sep-2016 07:18:09 GMT

Signature meaning: Approved

Leo Document ID = 8dc6cd7c-6e78-4134-9dc8-cc4750e454e4

Approver: [name] (AM\C243405)

Approval Date & Time: 08-May-2018 18:17:39 GMT

Signature meaning: Approved

2. ABBREVIATIONS

Abbreviations pertain to the Statistical Analysis Plan (SAP) only (not the tables, figures and listings [TFLs]).

AE	Adverse event
AUC	Area under the concentration versus time curve
AUC(0-t _{last})	Area under the concentration versus time curve from time zero to time t, where t is the last time point with a measurable concentration
AUC(0-∞)	Area under the concentration versus time curve from zero to infinity
%AUC(t _{last} -∞)	Percentage of AUC(0-∞) extrapolated
BQL	Below the quantifiable lower limit of the assay
C _{max}	Maximum observed drug concentration
CI	Confidence interval
C _{last}	Last quantifiable drug concentration
CL/F	Apparent total body clearance of drug calculated after extra-vascular administration
C _{nadir}	Nadir concentration
CRF	Case Report Form
CSR	Clinical Study Report
CRU	Clinical Research Unit
CV	Coefficient of variation
EC	Early Clinical
ECG	Electrocardiogram
e.g.	For example (Latin: exempli gratia)
FDA	Food and Drug Administration
ICH	International Council on Harmonisation
LLOQ	Lower limit of quantification
MedDRA	Medical Dictionary for Regulatory Activities
PD	Pharmacodynamic
PK	Pharmacokinetic
QTcB	QT interval corrected using Bazett's formula
QTcF	QT interval corrected using Fridericia's formula

SAP	Statistical Analysis Plan
SD	Standard deviation
SOP	Standard Operating Procedure
TFLs	Tables, Figures, and Listings
$t_{1/2}$	Half-life associated with the terminal rate constant (λ_z) in non-compartmental analysis
t_{nadir}	Time to reach nadir concentration
t_{max}	Time of maximum observed drug concentration
V_{ss}/F	Apparent volume of distribution at steady state after extra vascular administration
V_z/F	Apparent volume of distribution during the terminal phase after extra-vascular administration
WHO	World Health Organization

3. INTRODUCTION

This SAP has been developed after review of the Clinical Study Protocol (final version dated 10 September 2016).

This SAP describes the planned analysis of the safety, tolerability, pharmacokinetic (PK) and pharmacodynamic (PD) data from this study. A detailed description of the planned TFLs to be presented in the clinical study report (CSR) is provided in the accompanying TFL shell document.

The intent of this document is to provide guidance for the statistical , PD, and PK analyses of data. In general, the analyses are based on information from the protocol, unless they have been modified by agreement between Eli Lilly and Company and Covance Early Clinical (EC) Biometrics. A limited amount of information concerning this study (e.g., objectives, study design) is given to help the reader's interpretation. This SAP must be signed off prior to first subject administration for this study. When the SAP and TFL shells are agreed upon and finalized, they will serve as the template for this study's CSR.

This SAP supersedes the statistical considerations identified in the protocol ; where considerations are substantially different, they will be so identified. If additional analyses are required to supplement the planned analyses described in this SAP, they may be performed and will be identified in the CSR. Any substantial deviations from this SAP will be agreed upon between Eli Lilly and Company and Covance EC Biometrics and identified in the CSR. Any minor deviations from the TFLs may not be documented in the CSR.

This SAP is written with consideration of the recommendations outlined in the International Council on Harmonisation (ICH) E9 Guideline entitled Guidance for Industry: Statistical Principles for Clinical Trials¹ and the ICH E3 Guideline entitled Guidance for Industry: Structure and Content of Clinical Study Reports².

4. STUDY OBJECTIVES

4.1 Primary Objective

- To evaluate the relative bioavailability of a single 12 mg dose of LY3202626 as a tablet formulation (test formulation [T1-12]) compared to the capsule formulation (reference formulation [R]).

4.2 Secondary Objectives

- To evaluate the effect of a high-fat meal on the bioavailability of LY3202626 when administered as a single 12 mg dose of the test tablet formulation (T1-12).
- To assess the tolerability of LY3202626 when administered as a single 12 mg dose to healthy subjects.

4.3 Exploratory Objective

- To evaluate plasma A β 1-40 and A β 1-42 after a single 12 mg dose of LY3202626 as a tablet formulation (test formulation [T1-12]) and capsule formulation (reference formulation [R]).

5. STUDY DESIGN

This is a single-center, open-label, single-dose, randomized, 6-sequence, 3-period, crossover study in healthy subjects.

Screening will occur up to 28 days prior to the first dose of LY3202626.

Subjects will be admitted to the clinical research unit (CRU) on Day -1 of each period. In each period, subjects will be fasted overnight for at least 10 hours, and a single dose of 12 mg LY3202626, as either tablet (T1-12) in a fed state or fasted state or capsule (R) in a fasted state according to the randomization schedule, will be administered on the morning of Day 1. Blood sampling for assessment of LY3202626 PK and for PD assessments of A β 1-40 and A β 1-42 will be performed up to 168 hours postdose (Day 8). Subjects may be discharged from the CRU following completion of all 24-hour or 36-hour procedures on Day 2. If discharged after 24-hour procedures, subject will return to the CRU as an outpatient visit for the 36-hour PK sample collection. Subjects will return to the CRU daily for outpatient visits for PK sample collections Days 3 through 8. The washout period between dosing in 2 consecutive periods will be at least 10 days. A follow-up telephone call will be performed approximately 5 to 8 days after Period 3, Day 8.

Tolerability will be explored by clinical laboratory tests, vital sign measurements, 12-lead electrocardiograms (ECGs), and recording of adverse events (AEs).

The 3 dose administrations received by each subject will be:

- A = Reference (R): 12 mg LY3202626 capsule; administered in a fasted state
- B = Test (T1-12): 12 mg LY3202626 tablet; administered in a fasted state
- C = Test (T1-12): 12 mg LY3202626 tablet; administered in a fed state (Food and Drug Administration [FDA] high-fat meal)

Subjects will be randomized to 1 of 6 dose administration sequences (Table 1).

Table 1. Dose Administration Sequences

Sequence	Period 1	Period 2	Period 3
ABC	R fasted	T1-12 fasted	T1-12 fed
BCA	T1-12 fasted	T1-12 fed	R fasted
CAB	T1-12 fed	R fasted	T1-12 fasted
CBA	T1-12 fed	T1-12 fasted	R fasted
ACB	R fasted	T1-12 fed	T1-12 fasted
BAC	T1-12 fasted	R fasted	T1-12 fed

Abbreviations: R = reference (capsule formulation); T1-12 = test (tablet formulation)

Figure 1 illustrates the study design.

[figure not shown]

Figure 1. Illustration of Study Design for Protocol I7X-MC-LLCE

6. TREATMENTS

The following is a list of the study treatment abbreviations that will be used in the TFLs.

Study Treatment Name	Abbreviation	Treatment order in TFL
12 mg LY3202626 capsule (fasted)	R fasted	1
12 mg LY3202626 tablet (fasted)	T1-12 fasted	2
12 mg LY3202626 tablet (fed)	T1-12 fed	3

7. SAMPLE SIZE JUSTIFICATION

Up to approximately 24 healthy subjects may be enrolled to ensure that at least 20 subjects complete the study. This sample size is based on a calculation of precision of the estimated ratio of area under the concentration versus time curve (AUCs).

CCI

CCI

At the discretion of the investigator and sponsor, if multiple subjects who are randomized withdraw before study end, an additional 6 subjects (up to a total enrollment of 30 subjects) may be enrolled to ensure completion of 20 subjects. The replacement subject will be assigned the same dose administration sequence as the withdrawn subject's dose administration sequence (receiving each dose administration allocated).

8. DEFINITION OF ANALYSIS POPULATIONS

The "Safety" population will consist of all enrolled subjects, whether or not they completed all protocol requirements.

The PK analyses will be conducted on the full analysis set. This set includes all data from all subjects who received at least one dose of LY3202626.

The "Pharmacodynamic" population will consist of all subjects who received at least one dose of study drug and have evaluable PD data.

All protocol deviations that occur during the study will be considered for their severity/impact and will be taken into consideration when subjects are assigned to analysis populations.

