10.1. Sample Size Determination

Up to approximately 24 healthy subjects may be enrolled to ensure that at least 20 subjects complete the study. This sample size is based on a calculation of precision of the estimated ratio of area under the concentration versus time curve (AUCs).

CCI

At the discretion of the investigator and sponsor, if multiple subjects who are randomized withdraw before study end, an additional 6 subjects (up to a total enrollment of 30 subjects) may be enrolled to ensure completion of 20 subjects. The replacement subject will be assigned the same dose administration sequence as the withdrawn subject's dose administration sequence (receiving each dose administration allocated).

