10.3. Statistical Analyses

Statistical analysis of this study will be the responsibility of Eli Lilly and Company or its designee.

Pharmacokinetic analyses will be conducted on the full analysis set. This set includes all data from all subjects receiving at least 1 dose of LY3202626, according to the dose administration the subjects actually received. Safety analyses will be conducted for all enrolled subjects, whether or not they completed all protocol requirements.

Additional exploratory analyses of the data will be conducted as deemed appropriate. Study results may be pooled with the results of other studies for population PK analysis purposes to avoid issues with post-hoc analyses and incomplete disclosures of analyses.

No adjustments for multiple comparisons will be made.

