9. STATISTICAL METHODOLOGY

9.1 General

Data listings will be provided for all data that is databased. Summary statistics and statistical analysis will only be presented for data where detailed in this SAP. For continuous data, summary statistics will include the arithmetic mean, arithmetic standard deviation (SD), median, min, max and N; for log-normal data (e.g. the PK parameters: AUCs and maximum observed drug concentration [C_{max}]) the geometric mean and geometric coefficient of variation (CV%) will also be presented. For categorical data, frequency count and percentages will be presented. Data listings will be provided for all subjects up to the point of withdrawal, with any subjects excluded from the relevant population highlighted. Summary statistics and statistical analyses will generally only be performed for subjects included in the relevant analysis population. For the calculation of summary statistics and statistical analysis, unrounded data will be used.

Mean change from baseline is the mean of all individual subjects' change from baseline values. Each individual change from baseline will be calculated by subtracting the individual subject's baseline value from the value at the timepoint. The individual subject's change from baseline values will be used to calculate the mean change from baseline using a SAS procedure such as Proc Univariate.

Data analysis will be performed using SAS® Version 9.3 or greater.

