9.5 Safety and Tolerability Assessments

9.5.1 Adverse events

Where changes in severity are recorded in the Case Report Form (CRF), each separate severity of the AE will be reported in the listings, only the most severe will be used in the summary tables. A pre-existing condition is defined as an AE that starts before the subject has provided written informed consent and is ongoing at consent. A non-treatment emergent AE is defined as an AE which starts after informed consent but prior to the first dose. A treatment-emergent AE is defined as an AE which occurs postdose or which is present prior to dosing and becomes more severe postdose.

All AEs will be listed. Treatment-emergent AEs will be summarized by treatment, severity and relationship to the study drug. The frequency (the number of AEs, the number of subjects experiencing an AE and the percentage of subjects experiencing an AE) of treatment-emergent AEs will be summarized by treatment, Medical Dictionary for Regulatory Activities (MedDRA) version 19.1 system organ class and preferred term. The summary and frequency AE tables will be presented for all causalities and those considered related to the study drug. Any serious AEs will be tabulated.

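### Does a safety population of all enrolled subjects dilute the by-treatment adverse event percentages?

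*SAP*

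**What the plan says.** SAP section 8 defines the safety set without a dosing condition: the "population will consist of all enrolled subjects, whether or not they completed all protocol requirements". Protocol section 10.3 agrees: "Safety analyses will be conducted for all enrolled subjects, whether or not they completed all protocol requirements". Protocol Appendix 1 fixes the meaning of enrolment: "Subjects who are enrolled in the trial are those who have been assigned to a treatment". A subject who is randomised and leaves before the first dose is therefore in the safety set.

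The PK set in the same SAP section does require dosing: "This set includes all data from all subjects who received at least one dose of LY3202626". The pharmacodynamic set also requires at least one dose.

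For adverse events, SAP section 9.5.1 lists three frequencies: the number of events, the number of subjects affected, and "the percentage of subjects experiencing an AE) of treatment-emergent AEs will be summarized by treatment" (the stray bracket is in the source). It gives no denominator for the percentage. SAP section 9.1 adds the general rule: "Summary statistics and statistical analyses will generally only be performed for subjects included in the relevant analysis population". A detailed description of the planned tables "is provided in the accompanying TFL shell document", according to SAP section 3; that document is not among those reviewed.

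On numbers, Protocol sections 5.2 and 10.1 plan for about 24 subjects so that 20 complete, with six more possible if several withdraw, "up to a total enrollment of 30 subjects".

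**The concern.** Taken in sequence, the passages seem to lead to a poor denominator. The safety set is everyone assigned, summaries are made on the relevant set, and the event percentage is shown by treatment. On that reading each column is divided by all enrolled subjects. Someone who withdrew after Period 1 would count under two treatments never taken, and could not contribute an event to either.

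The incidence of treatment-emergent events is a stated secondary endpoint, so a systematic downward pull on it would matter. If withdrawals left different numbers dosed with the capsule, the fasted tablet and the fed tablet, a common denominator would also pull the three columns down by different amounts. The contrast with the PK and pharmacodynamic sets, both of which require a dose, makes the safety definition look like an oversight.

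**Working it through.** **Inputs**
- Initial enrolment 24, maximum 30, target 20 completers: Protocol 5.2 and 10.1, SAP 7.
- Completion means all three periods (Protocol 5.2), so each completer receives all three treatments.
- Doses taken by non-completers before leaving: not given. Assumed to be 0, 1 or 2, spread evenly over the treatments.

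**The plan's own figures.** The enrolment arithmetic agrees: 24 + 6 = 30. Going from 24 to 20 implies 4/24 = 16.7% non-completion. The precision calculation behind 20 completers is redacted and cannot be reproduced. The documents state no event percentage to check.

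**Formula.** If all N enrolled subjects are the denominator and n received the treatment, the relative understatement is 1 − n/N. With N − 20 non-completers taking d doses each, the average number dosed per treatment is n = 20 + (N − 20) × d/3.

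| Enrolled N | Non-completers | d = 0 | d = 1 | d = 2 |
|---|---|---|---|---|
| 24 | 4 | 1 − 20/24 = 16.7% | 1 − 21.33/24 = 11.1% | 1 − 22.67/24 = 5.6% |
| 30 | 10 | 1 − 20/30 = 33.3% | 1 − 23.33/30 = 22.2% | 1 − 26.67/30 = 11.1% |

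With no dropout the figure is 0%. As an example, take an assumed 5 affected subjects among 20 dosed: 5/20 = 25.0%, against 5/24 = 20.8% or 5/30 = 16.7%. A one-third loss needs maximum enrolment, exactly 20 completers, and all 10 non-completers missing that treatment.

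**Would a dosing condition on the safety set cure it?** Not by itself. If all 10 non-completers took one dose of some other treatment, all 30 subjects would still qualify, with 20 recipients: 1 − 20/30 = 33.3% again. The result turns on the column denominator, not on the population definition.

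**Do the treatments diverge?** In Protocol Table LLCE.2 each treatment appears twice in every period, and a replacement takes the withdrawn subject's sequence. Dropout unrelated to treatment therefore costs each treatment the same in expectation. When equal numbers are dosed, a common denominator leaves the ratio between columns unchanged: (x₁/N)/(x₂/N) = x₁/x₂ = (x₁/n)/(x₂/n).

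**Is the all-enrolled denominator prescribed?** SAP 8 says who belongs to the safety set. SAP 9.1 limits summaries, with a qualifier, to members of the relevant set; that restricts who may appear and does not place non-recipients under a treatment. SAP 9.5.1 says by treatment and stops there. Protocol 10.3.1.1 frames incidence in terms of each dose administration, which fits a denominator of subjects given that administration at least as well. No passage puts every enrolled subject in every column.

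**The case for a change.** The best case for a change is that the SAP should settle this itself. It says that it supersedes the protocol's statistical considerations, and the only population it offers for the event percentage is all enrolled subjects. Protocol 10.3 gives the PK analysis an as-received rule and gives safety none. A table shell that divided by subjects dosed would rest on no sentence in the SAP. The endpoint is secondary, and a clarifying line would cost almost nothing.

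Part of this stands. The denominator is unstated, the safety set carries no dosing condition, and a line in SAP 9.5.1 would do no harm. What does not stand is the step from silence to bias. The understatement arises only if the analyst picks a denominator that the text does not prescribe and that would be unusual in a crossover. The all-enrolled set also has a use: SAP 9.5.1 defines events starting between consent and the first dose as non-treatment-emergent and lists all events, and an undosed subject can have such an event.

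The consequences are limited as well. The secondary objective in SAP 4.2 is the tolerability of a single 12 mg dose, not a formal comparison of formulations or of fed and fasted dosing, and SAP 9.5.7 plans no inferential safety analysis. The numbers of events and of affected subjects do not depend on the denominator, all adverse events are listed, and subject disposition is listed under SAP 9.2, so a reader could see where the numbers dosed differ.

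**Conclusion.** No change is needed. The documents leave open the denominator of a descriptive table, and an analyst would ordinarily fill that gap with the number of subjects who received each treatment. On that choice the understatement is 0%.

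If all enrolled subjects were used instead, the relative understatement would run from 0% without dropout to at most 16.7% at 24 enrolled or 33.3% at 30. Those limits assume that at least 20 subjects complete, and the upper ends assume that every non-completer missed the treatment concerned. The intermediate values depend on an assumed number of doses before withdrawal, which the documents do not give. The conclusion also rests on the table shells following usual crossover practice; they were not available to check. The primary PK comparison uses a different analysis set and is not affected.
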